12.2. Analysis Populations

12.2.1. Screened Subjects

All subjects who sign an informed consent document will be included in the *screened subject* population.

12.2.2. Safety Set

All subjects who receive any amount of ¹⁸F-DCFPyL will be included in the *safety set*.

12.2.3. Evaluable Set

Evaluable subjects in Cohort A are those who provide a ¹⁸F-DCFPyL PET image result (positive or negative) and a corresponding RP histopathology result (positive or negative).

Evaluable subjects in Cohort B are those who provide a ¹⁸F-DCFPyL PET image result (positive or negative) and a corresponding biopsy histopathology result (positive or negative for each

subject), along with a conventional image that confirms the location of the histopathology sample.

12.2.4. Per Protocol Set

The *per protocol* set is the evaluable set, excluding subjects with major protocol deviations impacting efficacy endpoint(s).

12.2.5. PK Evaluable Set

Subjects who provide at least six of the nine scheduled blood samples will be evaluable for PK analysis of blood samples. Subjects with at least two of the three scheduled urines will be evaluable for PK analysis of urine samples.

12.3. Endpoints and Derivations

12.3.1. Sensitivity, Specificity, PPV, and NPV

Table 7 will be used to classify the combined pelvic lymph node packets (left or right) from Cohort A and biopsy from Cohort B according to its ¹⁸F-DCFPyL image result (positive or negative) generated from central imaging review and its histopathology result (positive or negative for prostate cancer) generated by the sites' pathology review. Nodes identified on ¹⁸F-DCFPyL PET/CT images in areas that were not removed in surgery for Cohort A will not be tabulated due to absence of histopathology.

Table 7: Classification of ¹⁸F-DCFPyL Imaging Result and Histopathology Result for Cohorts A and B Separately

	Histopatho	ology Result	
¹⁸ F-DCFPyL Image	Positive*	Negative	
Positive	ТР	FP	I(p)
Negative	FN	TN	I(n)
	R(p)	R(n)	Nı

TP=true positive; FP=false positive; FN=false negative; TN=true negative.

R(p) and R(n) denote the subjects with a positive or negative lobe or biopsy, respectively, based on histopathology. I(p) and I(n) denote the subjects with a positive and negative lesion, respectively, based on the ¹⁸F-DCFPyL image. N_1 indicates the number of subjects with evaluable pelvic lymph node packets from Cohort A or the number of subjects with evaluable biopsies from Cohort B.

*Positive histopathology should be for prostate cancer only.

The following statistics will be computed:

- Sensitivity = TP/R(p),
- Specificity = TN/R(n),
- Positive predictive value (PPV) = TP/I(p),
- Negative predictive value (NPV) = TN/I(n).

For Cohort A, a true positive or true negative must be determined from imaging and histopathology aligning on outcome overall.

12.3.2. Lesions Per Subject

The number of lesions detected on the ¹⁸F-DCFPyL PET/CT image in each of bone, lymph nodes, soft tissue, and prostate gland will be determined by each of the three central imaging core lab independent readers. The number of lesions per subject per region will be computed for each subject based on each reader's lesion count.

12.3.3. Change from Baseline

For laboratory data, baseline will be the screening/baseline value. Change from baseline will be computed as the pre-surgery/biopsy follow-up value minus the baseline value +1.

For ECG data, baseline will be the pre-dose value. Change from baseline will be computed as the post-dose value minus the pre-dose value +1.

For vital signs, baseline will be the pre-dose value. Change from baseline will be computed as the post-dose value minus the pre-dose value +1 and the pre-surgery/biopsy value minus the baseline value +1.

12.3.4. Pre-Treatment and Concomitant Medications

Pre-treatment medications are those administered prior to ¹⁸F-DCFPyL administration; concomitant medications are those administered from ¹⁸F-DCFPyL administration through last study visit.

12.3.5. Treatment-Emergent Adverse Events

Treatment-emergent adverse events will be those observed from the day of ¹⁸F-DCFPyL administration until 7 (\pm 3) days post study drug injection [if surgery (Cohort A) or biopsy (Cohort B) has not yet occurred] and 21 (\pm 7) days post biopsy in Cohort B.

12.4. Missing Data

No imputation of missing data will be applied.

12.5. Analyses

In general, continuous endpoints will be summarized by visit using summary statistics: sample size, mean, standard deviation, median, minimum, and maximum. Categorical endpoints will be summarized by visit using frequencies and percentages.

12.5.1. Subject Characteristics

A disposition table will be presented to show how many subjects were screened, the number and percentage of subjects in each population set, study completers, and early discontinuations along with reasons for discontinuation.

Baseline characteristics (age in years, categorical age [<65 years, \geq 65 years], race, gender, ethnicity, height [cm], weight [kg], BMI [kg/m²]) will be summarized for all analysis population

sets. Medical history verbatim terms will be coded using Medical Dictionary for Regulatory Activities (MedDRA). Subject frequencies and percentages will be tabulated by system organ class (SOC) and preferred term (PT) for all analysis population sets. Prior prostate cancer medical history will be summarized for all analysis populations. Type of CT, MRI or bone scans will be summarized along with days each occurred prior to study drug administration by all analysis populations.

Medications will be coded using the WHO Drug Dictionary. Pre-treatment medications will each be summarized by ATC4 class and generic name for all analysis population sets.

12.5.2. Efficacy Analysis

12.5.2.1. Primary Endpoint

Cohort A

The primary analysis in Cohort A will be addressed by computing point estimates and 95% twosided confidence intervals (CIs) for specificity first and if the null hypothesis is rejected for specificity then sensitivity will be tested next. Both outcomes are on the subject level (one overall outcome per subject) in the evaluable set. If the *per protocol* population exists then this analysis will be performed on the *per protocol* population as a supplemental analysis. The normal approximation to the binomial distribution will be used. Sensitivity and specificity will be computed for each of three central imaging core lab independent readers.

The null hypothesis for specificity will be rejected if the lower limit of the 95% CI exceeds 0.80 for at least two readers. If statistical significance is achieved for specificity where the null hypothesis is rejected, then sensitivity will be tested where the null hypothesis will be rejected if the lower limit of 95% CI exceeds 0.40 for the same two readers who rejected the null hypothesis for specificity.

A sensitivity analysis will be performed to allow any 2 of the 3 central readers to reject the null hypothesis for sensitivity only after specificity has been deemed a success. This analysis will not require the same 2 central readers to reject the null hypothesis for specificity and sensitivity. This analysis will be performed for the evaluable and per protocol populations.

12.5.2.2. Secondary Endpoints

The following secondary efficacy endpoint analyses will be generated on the evaluable set.

Point estimates and two-sided 95% CIs will be presented for the following secondary endpoints:

- PPV and NPV will be computed for the pelvic lymph node packets (one observation per subject for cohort A).
- Sensitivity of ¹⁸F-DCFPyL PET/CT imaging within sites of metastasis or local recurrence relative to histopathology (cohort B)
- PPV will be computed for the biopsies (one observation per subject for cohort B).

The normal approximation to the binomial distribution will be used for endpoints having one observation per subject. The null hypothesis will be rejected for each if the lower limit of the

95% CI exceeds 0.50 for at least 2 of the 3 central readers. Statistics will be computed for each of the three central imaging core lab independent readers.

Lesions per subject, as detected by ¹⁸F-DCFPyL PET/CT and conventional images will be summarized for each tissue type (bone, lymph nodes, soft tissue, and prostate gland) and each of the three central imaging core lab independent readers using evaluable subjects from both cohorts.

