12. STATISTICS

12.1. Sample Size

Approximately 262 subjects will be dosed in cohort A. No formal power calculations will be performed for cohort B; reliable estimates should be achievable from approximately 115 dosed. This results in a total sample size of approximately 377 subjects dosed in the study.

The primary analysis in Cohort A will test the co-primary endpoints of sensitivity and specificity of ¹⁸F-DCFPyL PET imaging relative to histopathology for metastatic disease in preprostatectomy patients. For each co-primary endpoint there will be three independent imaging readers. At least two of the three readers must reject the null hypothesis for specificity to be deemed a success. If specificity is a success, then the same two readers need to reject the null

hypothesis for sensitivity to reach overall success of the primary endpoint. The null hypotheses will be tested in the following order:

- 1. Specificity of ¹⁸F-DCFPyL PET/CT imaging relative to histopathology in cohort A H₀: $\pi_{Sp} = 0.80$ versus H₁: $\pi_{Sp} \neq 0.80$,
- 2. Sensitivity of ¹⁸F-DCFPyL PET/CT imaging relative to histopathology in cohort A

H₀: $\pi_{Se} = 0.40$ versus H₁: $\pi_{Se} \neq 0.40$

where π_{Se} is the true sensitivity and π_{Sp} is the true specificity of ¹⁸F-DCFPyL PET imaging.

A total of approximately 262 subjects from Cohort A will provide 80% power to reject the null hypothesis about sensitivity at the 5% significance level if the true sensitivity is at least 60% and at least 80% power to reject the null hypothesis about specificity at the 5% significance level if the true specificity is at least 87.8%. These calculations are based on the following assumptions:

• the probability of a positive histopathology sample in Cohort A is 20%,

The sample size is based on the normal approximation to the binomial distribution without a continuity correction⁴⁸:

$$n \ge \left\{ \frac{z_{\alpha/2} \sqrt{P_0(1-P_0)} + z_\beta \sqrt{P_1(1-P_1)}}{P_1 - P_0} \right\}^2$$

 P_0 are P_1 are values of sensitivity under the null and alternative hypotheses, respectively. After adjusting sensitivity and specificity separately by their corresponding prevalence values, a total in 236 evaluable subjects are needed in cohort A. Assuming 10% drop out or non-evaluable rate increases the required number of subjects in cohort A to approximately 262.

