The type I error rate will be preserved at 5% by requiring that both null hypotheses be rejected to draw the conclusion that F-DCFPyL is efficacious for imaging. The second primary endpoint is only tested if the first primary endpoint is rejected at the 0.05 level of significance per a fixed sequential method. If the first hypothesis fails to be rejected, no further testing will be conducted.

No formal power calculations will be performed for Cohort B since it is not a primary endpoint. Approximately 115 subjects will be dosed in this cohort.

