## 7.7. Analysis of Secondary Efficacy Endpoints

Analysis of secondary efficacy endpoints will be conducted regardless of the outcomes of the primary analyses. Diagnostic testing and imaging detection rates will be analyzed for the evaluable set. The PK parameters will be summarized for the PK blood set.

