#### 7.7.2. PPV and Sensitivity in Cohort B

Point estimates and two-sided 95% CIs for PPV and Sensitivity will be computed from the conventional guided biopsy obtained from subjects in Cohort B for the Evaluable Set. The normal approximation to the binomial distribution is planned assuming a null hypothesis of 0.5. If the assumptions are not met, then confidence intervals derived from an Agresti-Coull exact test will be used (See Section 7.2). Results will be computed for each of the three central imaging core lab independent readers.

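### Protocol 12.5.2.2 tests Cohort A nodal NPV against 0.50, a bar that an uninformative scan clears at the assumed 20% prevalence; the SAP omits the rule without recording the change

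*Protocol*

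**What the plan says.** Protocol 12.5.2.2 lists the secondary endpoints that receive point estimates and two-sided 95% intervals. For Cohort A, "PPV and NPV will be computed for the pelvic lymph node packets (one observation per subject for cohort A"). For Cohort B, "PPV will be computed for the biopsies (one observation per subject for cohort B"), and Cohort B sensitivity is in the same list. On method: "The normal approximation to the binomial distribution will be used for endpoints having one observation per subject". The null is then rejected for each endpoint if the lower limit of the "95% CI exceeds 0.50 for at least 2 of the 3 central readers". No reason is given for 0.50.

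Protocol 12.1 sizes Cohort A on the assumption that "the probability of a positive histopathology sample in Cohort A is 20" per cent. The co-primary nulls there are specific to the endpoint: 0.80 for specificity and 0.40 for sensitivity.

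SAP 7.7.1 gives Cohort A PPV and NPV as estimates with 95% intervals, and states no null value and no two-of-three-reader criterion. SAP 7.7.2, on Cohort B PPV and sensitivity, says: "The normal approximation to the binomial distribution is planned assuming a null hypothesis of 0.5". SAP Section 10, which lists differences from the protocol, does not mention the 0.50 rule.

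**The concern.** PPV and NPV depend on prevalence as well as on the scan. When 80% of subjects have negative nodes, a negative call is right 80% of the time even if it is unrelated to histology. A bar of 0.50 lies far below that level, so a rejected null for NPV cannot separate a useful scan from a useless one. The same 0.50 lies far above the no-information PPV of 0.20, so one number does two quite different jobs.

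What is at stake is how a secondary result is read. A statement that the NPV null was rejected by at least two readers would look like evidence of performance and would be none. Because the protocol states the rule and the SAP leaves it out without recording a change, it is unclear at reporting whether that statement is part of the planned analysis.

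**Working it through.** **Inputs.** From Protocol 12.1: prevalence 0.20; minimum powered alternative of sensitivity 0.60 and specificity 0.878; nulls 0.40 and 0.80; 236 evaluable in Cohort A; about 115 dosed in Cohort B. From Protocol 12.5.2.2: normal-approximation 95% interval and the 0.50 bar.

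**Reproducing the plan's own figure.** The protocol's formula, two-sided 5% with 80% power, gives 47.09 node-positive subjects for sensitivity (0.40 against 0.60), and 47.09/0.20 = 235.5. For specificity (0.80 against 0.878) it gives 184.5 node-negative subjects, and 184.5/0.80 = 230.6. The larger rounds up to 236, and 236/0.9 = 262.2, matching the stated 236 and approximately 262. So 20% prevalence is the value the design rests on.

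**Formulas.** With prevalence π, sensitivity Se and specificity Sp:

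- PPV = π·Se / [π·Se + (1−π)(1−Sp)]
- NPV = (1−π)·Sp / [(1−π)·Sp + π(1−Se)]
- Lower limit = p − 1.96·√(p(1−p)/m), where m is the number of positive scans (PPV) or negative scans (NPV)

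Pass probabilities are exact binomial sums over the counts whose lower limit exceeds 0.50.

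**NPV, uninformative scan (Se = 1 − Sp).** NPV = 1 − π = 0.80 whatever share of scans is read positive.

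- All 236 read negative: 0.80 − 1.96·√(0.16/236) = 0.80 − 0.051 = 0.749.
- Coin-flip reader, about 118 negatives: 0.80 − 1.96·√(0.16/118) = 0.80 − 0.072 = 0.728.
- With 118 negatives the bar needs only 70 correct: 70/118 = 0.593, lower limit 0.593 − 0.089 = 0.505. The expected number correct is 0.80 × 118 = 94.
- The pass probability is about 100% per reader when up to 70% of scans are read positive, and 89% when 90% are. It stays above 99% at 30% prevalence and is about 60–79% at 40%.

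**NPV, scan at the co-primary nulls (0.40/0.80).** NPV = 0.64/(0.64 + 0.12) = 0.842 on 236 × 0.76 ≈ 179 negative scans. Pass probability is about 100% per reader.

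**PPV, minimum powered alternative (0.60/0.878).** PPV = 0.12/(0.12 + 0.0976) = 0.551 on 236 × 0.2176 ≈ 51 positive scans. With 51 positives, 32 correct gives a lower limit of 0.495 and 33 gives 0.516, so 33 are needed.

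| Prevalence | PPV | Expected positive scans | Pass probability per reader |
|---|---|---|---|
| 15% | 0.465 | 46 | 1% |
| 20% | 0.551 | 51 | 10.8% (51 fixed), 12.5% (count random) |
| 25% | 0.621 | 57 | 48% |
| 30% | 0.678 | 63 | 83% |

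At 20% prevalence, the two-of-three rule gives about 4% if readers are independent (3 × 0.1248² × 0.8752 + 0.1248³ = 0.043) and 12.5% if they agree completely. At sensitivity 0.60 and 20% prevalence, the per-reader pass probability exceeds 50% from a specificity of about 0.92 and reaches 80% at about 0.94.

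**Cohort B PPV (assumptions, not document figures).** The documents give no biopsy-positive rate. Applying Cohort A's 10% loss to 115 gives about 104 evaluable. An uninformative scan's PPV equals the biopsy-positive rate, so with between half (52) and all (104) of the scans read positive:

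| Assumed biopsy-positive rate | Pass probability per reader, uninformative scan |
|---|---|
| 60% | 36–57% |
| 70% | 88–99% |
| 80% | about 100% |

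**The case against.** The strongest reply is that the SAP has already dealt with this. It was written on protocol amendment 2 (November 2017) and is dated September 2018. It states 0.5 for Cohort B and leaves it out for Cohort A, which looks deliberate. If the SAP governs, Cohort A PPV and NPV are descriptive and no empty NPV rejection arises. That stands as far as it goes, but Section 10 exists to record such departures and does not record this one, so the protocol rule has not been withdrawn.

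Second, a null need not be the chance value. The co-primary bars are themselves performance benchmarks, and PPV above 0.50 has a plain meaning: a positive scan is right more often than wrong. The 0.60 and 0.878 are also minimum values; the plan says at least. This stands. A reader might infer that the PPV test is as empty as the NPV test, but the figures show only low power at one set of values.

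Three further inferences are tempting and not supported:

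- **That SAP 4.3 and 7.7 conflict.** SAP 4.3 says "If the first hypothesis fails to be rejected, no further testing will be conducted", but this closes a paragraph on the co-primary sequence. SAP 7.7 says "Analysis of secondary efficacy endpoints will be conducted regardless of the outcomes of the primary analyses". In context the two are compatible.
- **That a secondary result could support an efficacy conclusion after a failed primary.** Protocol 12.1 and SAP 4.3 and 7.5 tie that conclusion to rejecting both co-primary nulls, and no text attaches it to a secondary endpoint.
- **That Cohort B is shown to have the same fault.** SAP 7.7.2 contains no NPV and no explicit rejection rule. Sensitivity does not depend on prevalence, so the argument does not reach Cohort B sensitivity. For Cohort B PPV, the weakness depends on a biopsy-positive rate that the documents do not give.

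**Conclusion.** The point holds for Cohort A. As the protocol is written, the nodal NPV test passes about 100% of the time per reader for a scan with no information, and for a scan at both co-primary null values. This rests on the plan's own 20% prevalence and 236 evaluable subjects, and holds up to about 30% prevalence.

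For PPV the finding is weaker: about 11–12% per reader at the minimum powered alternative and 20% prevalence, rising quickly with prevalence or specificity. That is low power against a defensible benchmark.

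The difference between Protocol 12.5.2.2 and SAP 7.7.1 is real and unrecorded. For Cohort B PPV the most that can be said is conditional: if most biopsies are positive, exceeding 0.5 is weak evidence about the scan. All of this concerns secondary endpoints.

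**What to change.** 1. In Protocol 12.5.2.2, remove the 0.50 rejection rule for Cohort A PPV and NPV. Report estimates with 95% intervals for each reader, as SAP 7.7.1 already does.
2. Beside them show the no-information reference from the same subjects: the observed histology-positive proportion for PPV, and one minus it for NPV. Present it as a descriptive reference without a test, since it is itself estimated from those subjects and has sampling error.
3. List the removal in SAP Section 10.
4. For Cohort B PPV (SAP 7.7.2), present the estimate and interval beside the observed biopsy-positive proportion, and state that exceeding 0.5 is not by itself evidence of performance.

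The cost is wording and one extra line in the secondary table. The sponsor gives up a nominal secondary test result. Sample size, data collection and the co-primary tests do not change.

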12.5.2.3. Exploratory Analyses

Analyses will be generated on the evaluable set for the following exploratory endpoints:

- The number of lesions per subject will be plotted against baseline PSA and baseline testosterone for each of the three central imaging core lab independent readers using evaluable subjects from both cohorts.
- SUV_{max}, SUV_{peak} and SUVr will be summarized for each tissue type (e.g., bone, lymph nodes, soft tissue, and prostate gland) and each of the three central imaging core lab independent readers using evaluable subjects from both cohorts. The relationship between SUVr in prostatic lesions and baseline PSA and testosterone levels, and Gleason score at time of radical prostatectomy will be evaluated.
- Sensitivity, SUV_{max}, SUV_{peak}, and SUV_r will be computed for the following subgroups in Cohort A:
 - Previous radiation therapy (yes/no)
 - Previous hormonal therapy (yes/no)
 - Previous chemotherapy (yes/no)
- SUV_{max}, SUV_{peak}, and SUV_r will be summarized with positive and negative histopathology. Each will be summarized by Gleason score for the single or dominant prostate tumor nodule.
- The clinical management plans before and after review of ¹⁸F-DCFPyL PET/CT scans will be summarized.

An exploratory analysis of PPV of ¹⁸F-DCFPyL PET/CT imaging in subjects who are excluded from the *evaluable set* but have corresponding histopathology outside the planned protocol procedure will be performed on the *safety set*.

12.5.3. Safety

All safety parameters will be presented for the safety set.

12.5.3.1. Exposure

Volume administered (mL) and activity administered (mCi) will be summarized using the Safety Set and the Evaluable Set.

12.5.3.2. Adverse Events

Adverse event verbatim terms will be coded using MedDRA. The frequency and percentage of subjects with an adverse event and the number of events will be summarized by SOC and PT. Adverse events will also be summarized by severity and, separately, by relationship to treatment. Serious adverse events, adverse events leading to study discontinuation and adverse events leading to death will be listed.

12.5.3.3. Clinical Laboratory

Observed values and changes will be tabulated using summary statistics in the safety set.

12.5.3.4. ECG

Observed values and changes will be tabulated for each visit using summary statistics. Shift tables comparing pre- to post-dosing categorical ECG values will be presented using the *safety set*.

12.5.3.5. Vital Signs

Observed values and changes will be tabulated using summary statistics in the safety set.

12.5.4. Pharmacokinetics

Mean (±SD) and individual activity-time plots will be presented for blood (mCi/mL), urine (% injected dose excreted per collection interval) and selected organs/tissues, including "whole body" (% injected dose at each scanning time-point). Summary statistics (sample size [N], arithmetic mean, geometric mean, median, SD, minimum, and maximum) will be presented by timepoint for each of blood, urine and selected organs/tissues, including "whole body".

Summary statistics will be presented for C_{max} , area under the curve (AUC), total clearance (CL), steady-state volume of distribution (V_{ss}), and mean residence time (MRT) for the subset of subjects (PK evaluable set).

